#### **5.3. Drug Supplies**

In this clinical trial, study drug or investigational agent refers to axitinib and placebo.

## 5.3.1. Formulation and Packaging

Axitinib will be supplied as 1 mg and 5 mg film-coated tablets for oral administration in light-protecting bottles. Placebo will match all dose formulations.

## 5.3.2. Preparation and Dispensing

Axitinib and matching placebo will be dispensed as tablets in opaque plastic bottles to protect the compounds from light. Axitinib is a hazardous drug (due to possible reproductive toxicity), and should be handled according to the recommended procedures described in the current edition of the American Society of Hospital Pharmacists (ASHP), Technical Assistance Bulletin on Handling Cytotoxic and Hazardous Drugs, American Hospital Formulary Service (AHFS) Drug Information (1999) and its references. Procedures described in each institution's pharmacy or hospital standard operating procedure manual should be followed when handling hazardous drugs.

#### 5.3.3. Administration

Patients will receive blinded study drug: Axitinib or blinded matching placebo identical in appearance to the active study drug twice daily.

Patients will receive a starting dose of 5 mg of axitinib or placebo twice daily taken orally with or without food. Dose adjustments, including dose increase or dose reduction will be based on adverse events experienced by the individual patient. Study drug will be taken beginning on Day 1 of the study. Doses should be taken approximately 12 hours apart continuous dosing. Patients should be instructed to take their doses at approximately the same times each day. If a patient vomits or misses a dose, an additional dose should not be taken. The next prescribed dose should be taken at the usual time. Missed or vomited doses must be indicated in the source documents and Case Report Forms (CRFs). Study drug will be administered in cycles of 4 weeks in duration.

Patients who tolerate axitinib or placebo with no adverse events related to study drug above CTCAE Grade 2 for a consecutive 2-week period may have their dose increased by one dose level to maximum of 10 mg BID (unless the patient's BP is >150/90 mm Hg or the patient is receiving antihypertensive medication). The clinical judgment of the treating investigator should be exercised in titrating axitinib/placebo dose.

Patients experiencing drug reaction should undergo dose modification as recommended in Section 5.3.4.

Once the dosage is reduced, it can be uptitrated again.

Concomitant medications that are known to substantially inhibit the enzyme, CYP3A4/5, should be avoided as much as medically possible on this study as in Section 5.5.1. If a strong CYP3A4/5 inhibitor must be co-administered, based on investigator judgment, the dose of study drug (axitinib/placebo) should be decreased by one or more dose levels.

Version - #10 Mar. 21, 2017

Table 2 Available Axitinib/Placebo Dose Levels

Dose Level	Dose	Dispensed As
+2	10 mg BID	2 X 5 mg Tablets BID
+1	7 mg BID	1 X 5 mg Tablet BID + 2 X 1mg Tablets BID
0 (Starting Dose)	5 mg BID	1 X 5 mg Tablet BID (twice daily)
-1	3 mg BID	3 X 1 mg Tablets BID
-2	2 mg BID	2 X 1 mg Tablets BID
-3	1 mg BID	1 X 1 mg Tablet BID

## 5.3.4. Dose Interruption and Reduction

Adverse events and other symptoms will be graded according to the current CTCAE v4.0 (See URL: http://ctep.cancer.gov/reporting/ctc.html).

## 5.3.4.1. Management of Axitinib/Placebo-Related Adverse Events

This section contains management of adverse events except hypertension and proteinuria which are discussed in subsequent sections.

The criterion for dose modification for study-drug-related adverse events is summarized in the table below:

Table 3 Criteria for Dose Modification for Axitinib/Placebo – Related Adverse Events Other Than Hypertension Or Proteinuria

Related Adverse Events	Intervention
Grade 1	Continue at same dose level.
Grade 2*	Continue at same dose level or decreased dose to one
	lower dose level. a)
Grade 3*	Interrupt dosing; re start at one or two lower dose level
	as soon as improvement to CTCAE Grade ≤1 or
	baseline. b) Discontinue dosing in case of grade 3
	persisting for $\geq 2$ weeks or grade 3 despite dose
	reduction to 1 mg BID.
Grade 4 or RPLS**	Discontinue dosing

\* Patients who have a grade 3 arterial event, grade 3 hemorrhagic event, grade 3 perforation/fistula, grade 3 palmar-planter erythrodysesthesia syndrome (PPE), or persistent grade 2 PPE despite dose reduction to 1 mg BID, should be discontinued dosing.

- a) Dose may be decreased to one lower dose level if the investigator considers it is difficult to continue treatment at same dose level.
- b) Dose may be decreased to two lower dose level if the investigator considers it is difficult to continue treatment at one lower dose level.

\*\* Treatment interruption for patients with signs/symptoms of reversible posterior leukoencephalopathy (RPLS). RPLS is a neurological disorder which can present with headache, seizure, lethargy, confusion, blindness and other visual and neurologic disturbances. Mild to severe hypertension may be present. Magnetic resonance imaging is necessary to confirm the diagnosis of RPLS. In case of confirmed diagnosis discontinue permanently.

Dose may also be interrupted or decreased at the discretion of the investigator even if none of the above criteria applies.

Guidelines for dose reductions for specific adverse events are provided in the following sections.

## 5.3.4.2. Axitinib/Placebo Dose Reduction for Hypertension

Patients treated with axitinib/placebo will be issued blood pressure cuffs (provided by Sponsor) for home monitoring and instructed to measure their blood pressure prior to taking each dose of study drug (twice daily) for the first 3 months, and once a week thereafter. Following dose modification of study drug or anti-hypertensive medication, or changes of anti-hypertensive medication, patients must restart blood pressure measurements prior to taking each dose of study drug for the first 3 months and once a week thereafter. All BP measurements will be recorded in a diary by the patient themselves and brought to the nurse or study coordinator at each clinic visit. Patients should be instructed by the study staff to contact their investigator immediately for guidance if their sBP rises above 150 mm Hg, or dBP rises above 100 mm Hg, or if they develop symptoms perceived to be related to elevated BP (eg, headache, visual disturbance). See below for dose modifications for hypertension.

New or additional antihypertensive therapy (See Section 5.5.1, Concomitant Medication) should be started if 2 BP readings, taken at site and separated by at least 5 minutes in the seated position after the patient has been sitting quietly for 5 minutes, show the following: 2 sBP readings >150 mm Hg or 2 dBP readings >100 mm Hg. Alternately, the dose of existing antihypertensive medication(s) may be increased. If the patient is already on maximal antihypertensive treatment, the axitinib/placebo dose should be reduced by 1 dose level.

Patients who have 2 sBP readings, separated by at least 5 minutes, greater than 160 mm Hg, or 2 dBP readings, separated by at least 5 minutes in the seated position after the patient has been sitting quietly for 5 minutes, greater than 105 mm Hg, will have treatment with axitinib/placebo interrupted. (Note: if axitinib/placebo is interrupted, patients receiving antihypertensive medications should monitor closely for hypotension and restart axitinib/placebo at one lower dose level as soon as BP is ≤150/100 mm Hg. Plasma half-life of axitinib is 2-4 hours and BP usually decreases within 1-2 days following dose interruption.) Treatment with axitinib/placebo should be restarted at 1 lower dose level as soon as the sBP reduces to less than or equal to 150 mm Hg and the dBP reduces to less than or equal to 100 mm Hg.

Patients who develop recurrent systolic hypertension (2 BP readings separated by at least 5 minutes show sBP >150 mm Hg) or recurrent dBP >100 mm Hg following previous axitinib/placebo dose reduction should undergo another dose reduction by one dose level.

Patients removed from treatment for intolerable toxicity should still be followed with regular tumor assessments until recurrence or occurrence of a secondary malignancy or start of new treatment, and for survival thereafter. Guidance on dose interruption and reduction for

hypertension is summarized in the table below. The BP readings stated in this table is based on BP measurement taken at the site.

 Table 4
 Hypertension Management Plan for Axitinib/Placebo

Degree of Bloo	Management		
Systolic Blood Pressure  2 BP readings separated by at least 5 minutes show sBP  >150 mm Hg	OR	Diastolic Blood Pressure  2 BP readings separated by at least 5 minutes show dBP >100 mm Hg	If not on maximal antihypertensive treatment, institute new or additional antihypertensive medication* and maintain dose of axitinib/placebo. If on maximal antihypertensive treatment, reduce axitinib/placebo to one lower dose level.
2 BP readings separated by at least 5 minutes show sBP >160 mm Hg	OR	2 BP readings separated by at least 5 minutes show dBP >105 mm Hg	Interrupt dosing**; Adjust antihypertensive medication; As soon as BP is less than or equal to 150/100 mm Hg, restart axitinib/placebo at one lower dose level.
Recurrent hypertension following previous dose reduction (2 BP readings separated by at least 5 minutes show sBP >150 mm Hg)	OR	Recurrent dBP >100 mm Hg (2 BP readings separated by at least 5 minutes) following previous dose reduction	Repeat axitinib/placebo dose reduction by one lower dose level.

\* If no contraindication – consider preferred anti-hypertensive monotherapy: Angiotensin system inhibitors (ASI) or preferred combination anti-hypertensive therapy: Diuretic and angiotensin system inhibitor [please check local guidelines]

Based on current international guidelines: ASI- Angiotensin Converting Enzyme (ACE) Inhibitor or Angiotensin receptor blocker; Diuretics; Beta-blocker or Calcium antagonists: All suitable and recommended for initiation + maintenance of antihypertensive treatment as monotherapy or in some combinations. Additional aspects for consideration within this study:

- No drug-drug interaction between axitinib and ASI expected (e.g. enalapril, captopril, losartan, valsartan). Retrospective data [McKay et al.J Clin Oncol 32, 2014 (suppl 4; abstr 437)] indicate that ASI may improve outcome in patients with renal cell cancer.
- No interference between axitinib and beta blockers (atenolol, metoprolol, labetalol), or diuretics (hydrochlorothiazide, furosemide) expected.
- Not first choice based on potential interference with axitinib plasma level: calcium channel blockers (verapamil) and to a lesser extent nifedipine, nicardipine, and diltiazem.
- Other calcium channel blockers (amlodipine, bepridil, felodipine) are less likely to interfere with axitinib plasma levels.
- \*\* If axitinib/placebo is interrupted, patients receiving antihypertensive medications should be monitored closely for hypotension. Plasma half-life of axitinib is 2-4 hours and BP usually decreases within 1-2 days following dose interruption.

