## **Trial Design:**

This is a prospective, randomized, double-blind placebo controlled Phase 3 trial of oral axitinib starting at 5 mg twice daily vs. placebo given for up to 3 years, with a minimum of 1 year. The dose may be increased or decreased depending on individual patient tolerance of axitinib.

A total of approximately 700 patients will be randomized in a 1:1 ratio between axitinib vs placebo. Patients should begin study treatment within 7 days after randomization. Randomization will occur no sooner than 4 weeks post-nephrectomy and no later than 12 weeks post-nephrectomy.

Recurrence or occurrence of a secondary malignancy will be followed up, by clinic visit (See Section 6.4 for further details), until the time of the final analysis (regardless of the duration of treatment) every 16 weeks for the first 3 years from initiation of study treatment (also, at the end of treatment) and every 6 months thereafter for the remainder of the follow-up period.

All patients will be followed up for OS status (regardless of the duration of treatment) every 16 weeks until the time for final DFS analysis. Survival status can be ascertained by telephone contact. At the time of final DFS analysis, OS results will be analyzed and summarized.

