- 13. **CT or MRI of brain**: To be done at screening and the images sent to the IRC for retrospective confirmation. Patients with any evidence of brain metastasis must be excluded from the study. Images should be submitted for IRC review before Week 8 post-nephrectomy to allow for return of the results before Week 12 and in the event a repeat scan is needed. Brain CT or MRI within 12 weeks prior to randomization is acceptable regardless of whether it is before or after nephrectomy. Subsequent CT or MRI of brain is not required, but may be performed if clinically indicated.
- 14. **Tumor Imaging**: Pre-surgery images are requested, if available, and should be submitted for IRC review. Screening visit imaging will be reviewed by IRC, designated by the sponsor, and must be performed at least 3 weeks after nephrectomy. Images should be submitted for IRC review before Week 8 post-nephrectomy to allow for return of the results before Week 12 and in the event a repeat scan is needed. CT or MRI of the chest, abdomen and pelvis for DFS should be performed (regardless of the duration of treatment) every 16 weeks for the first 3 years from initiation of study treatment (also, at the end of treatment). Allowable window for assessment is +/- 7 days. Thereafter,

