#### Footnotes for Schedule of Assessments

- imaging should be repeated every 6 months for the duration of the DFS follow-up period. Additional imaging of potential disease sites should be performed whenever recurrence or occurrence of a secondary malignancy is suspected. Bone scan (confirmatory imaging in addition to bone scan may be required), if clinically indicated.
- 15. **Histo-/cytopathology:** Local histopathology confirmation of eligibility is required. After randomization, in cases for which there is site confirmation of recurrence or occurrence of a secondary malignancy in the absence of IRC imaging confirmation, available local histo-/cytopathology reports should be submitted to the IRC for review.
- 16. **Study Randomization**: Patients must be randomized by 12 weeks after nephrectomy. Patient eligibility must be confirmed by IRC review for imaging and by a sponsor designated laboratory. Patients must be randomized based on the assessment by the IRC when there is a discrepancy between the local and the IRC imaging review.
- 17. **Study Treatment**: Should be started within 7 days after randomization. It is not necessary to repeat the Day 1 procedures if treatment is not started on the same day as randomization. Patients will receive either axitinib tablets at a starting dose of 5 mg BID or placebo according to randomization. The axitinib/placebo dose may be adjusted up or down according to individual patient tolerance per protocol dose modification procedure. Study drug are dispensed on Day 1 of each cycle.
- 18. **Adverse Events (AEs)**: Will be collected from the first day of study treatment until at least 28 days after the last on-study drug administration (Allowable window for assessment is 0/+7 days.), or until all serious or study drug-related toxicities have resolved or are determined to be "chronic" or "stable," whichever is later. Serious adverse events should be monitored and reported from the time that the patient provides informed consent and as described in the protocol.
- 19. Study Drug Compliance: The study drug bottle(s) including any unused tablets will be returned to the clinic for drug accountability.
- 20. **Prior/Concomitant Medications and Treatments**: Will be recorded from the time the patient has signed informed consent until 28 days after last treatment. Allowable window for assessment is 0/+7 days. Anti-tumor therapy should be recorded even after 28 days after last treatment.

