#### 3. TRIAL DESIGN

This is a prospective, randomized, double-blind placebo controlled Phase 3 trial of oral axitinib starting at 5 mg twice daily vs. placebo given for up to 3 years, with a minimum of 1 year. The dose may be increased or decreased depending on individual patient tolerance of axitinib.

A total of approximately 700 patients will be randomized in a 1:1 ratio between axitinib vs placebo. Patients should begin study treatment within 7 days after randomization. Randomization will occur no sooner than 4 weeks post-nephrectomy and no later than 12 weeks post-nephrectomy.

Follow-up for recurrence (distant or local recurrence of RCC) or occurrence of a secondary malignancy (occurrence of a second primary cancer other than RCC) must be collected at each clinic visit as per protocol. All patients will be followed up (regardless of the duration of treatment) until the time for the final analysis, every 16 weeks for the first 3 years from initiation of study treatment (also, at the end of treatment) and every 6 months thereafter for the remainder of the follow-up period, by clinic visit (See Section 6.4 for further details).

All patients will be followed up for OS status (regardless of the duration of treatment) every 16 weeks until the time for final DFS analysis. Survival status can be ascertained by telephone contact. At the time of final DFS analysis, OS results will be analyzed and summarized.

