## 6.4. Recurrence or occurrence of secondary malignancy and Survival Follow-Up

Follow-up for recurrence or occurrence of a secondary malignancy must be collected at each clinic visit as per protocol. All patients will be followed up (regardless of the duration of treatment) until the time for final analysis, every 16 weeks for the first 3 years from initiation of study treatment (also, at the end of treatment) and every 6 months thereafter for the remainder of follow-up period\*. If new anti tumor therapy is initiated for either recurrence or occurrence of a secondary malignancy at any time during this period, this and all other pertinent data obtained should be recorded on the appropriate CRFs. The final analysis of primary endpoint (DFS) will be performed when approximately 245 DFS events have been reached.

\* Patients who complete 3-year treatment will be followed up for DFS every 6 months from the date of CT or MRI at the end of study treatment.

Patients who withdraw from treatment before DFS events will be followed up for DFS every 16 weeks from the date of CT or MRI at the withdrawal. After 3 years from initiation of study treatment, CT or MRI for DFS will be performed every 6 months from the first scan date that is performed after more than 3 years from initiation of study treatment.

All patients will be followed up for OS status (regardless of the duration of treatment) approximately every 16 weeks from DFS events until the time for final DFS analysis. Survival status can be ascertained by telephone contact.

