#### 7. ASSESSMENTS

#### 7.1. Efficacy Assessments

Local and the IRC imaging tumor assessments are to be performed between week 3-8 post-nephrectomy. Brain CT or MRI within 12 weeks prior to randomization is acceptable regardless of whether it is before or after nephrectomy.

During the trial, local and the IRC imaging tumor assessments will be performed (regardless of the duration of treatment) every 16 weeks during the first 3 years of study (also, at the end of treatment) and every 6 months thereafter until the time for final analysis, or recurrence or occurrence of a secondary malignancy, whichever comes first.

Investigators are encouraged to await the result of the IRC assessment before making treatment decisions for patients who require palliative radiotherapy because of suspected recurrence or occurrence of a secondary malignancy unless clinical considerations require immediate intervention eg, in the case of brain metastases. In the event that an investigator determines recurrence or occurrence of a secondary malignancy based on local imaging reviews and/or local histo-/cytopathology reports, the patient must continue to receive tumor assessments until the IRC determines recurrence or occurrence of a secondary malignancy.

Local and IRC imaging assessments at screening and during the trial will include CT or MRI of the brain, chest, abdomen and pelvis, and other applicable sites. Further imaging techniques e.g., bone scan, are to be performed as clinically indicated if metastases are present or suspected.

For patients who present with findings suggestive of a tumor recurrence or secondary malignancy, histo-/cytopathological confirmation of the diagnosis should be obtained except in patients whose suspicious lesions are deemed by the investigator not to be amenable to biopsy. Such available local histo-/cytopathology reports should be submitted to the IRC for review in cases for which there is site confirmation of recurrence or occurrence of a secondary malignancy in the absence of IRC imaging confirmation. For patients with an isolated, suspected intracranial recurrence, histologic documentation of recurrence in surgically accessible lesions is highly recommended, but not required. For such patients, document the recurrent disease using MRI or CT if MRI is not generally available or is contraindicated.

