**Statistical Analysis Plan**

---

Subjects who discontinue study treatment will continue to be followed-up for DFS and OS until the time they have an event, or until the time of final analysis for DFS and OS. Subjects who withdraw from the study and are lost to follow-up will not be replaced. Surviving subjects without a DFS event and/or OS event at the time of the final analysis will have their DFS censored as described in Appendix A. All other missing data will be left as missing with the following exception as described in Section 6.2.1.

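### Two toxicity sections of the protocol stop tumor scans at new treatment, against the follow-up rule elsewhere, and could starve the SAP Table 4 sensitivity analysis of data

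*Protocol*

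**What the plan says.** Protocol 5.3.4.2 (hypertension) and 5.3.4.3 (proteinuria) carry the same sentence. Patients removed from treatment for intolerable toxicity are to have regular tumor assessments "until recurrence or occurrence of a secondary malignancy or start of new treatment, and for survival thereafter". Neither section defines new treatment.

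Four other places set the follow-up rule without that stop:

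- Protocol 6.4 follows every patient to the final analysis and adds: "Patients who withdraw from treatment before DFS events will be followed up for DFS every 16 weeks".
- Protocol 7.1 names only the final analysis, recurrence or secondary malignancy as end points for imaging.
- Footnote 14 of the Schedule of Assessments says that CT or MRI "should be performed (regardless of the duration of treatment) every 16 weeks for the first 3 years from initiation of study treatment", after which "imaging should be repeated every 6 months for the duration of the DFS follow-up period".
- SAP 6.2 states: "Subjects who discontinue study treatment will continue to be followed-up for DFS and OS until the time they have an event", or until the final analysis.

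The protocol Summary and Section 3 both send the reader to Section 6.4 for follow-up details.

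**The concern.** The primary DFS analysis censors at the last IRC-reviewed scan before anti-tumor therapy (SAP 5.1 and Appendix A, Table 1). The sensitivity analysis in Protocol 9.2.1, SAP 7.3.1 and Appendix A, Table 4 removes that rule, to show the result when new therapy is ignored. It can do so only if patients are still observed after new therapy starts. A site that takes 5.3.4.2 or 5.3.4.3 at its word would switch such a patient to survival follow-up and stop imaging. The check on the censoring rule would then lack the data that distinguish it from the primary analysis. Scans not taken cannot be recovered later.

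**Working it through.** **1. Do the texts conflict?** Take a patient removed for toxicity, without a DFS event, who then starts new anti-tumor therapy.

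| Place | Do scans continue? |
|---|---|
| Protocol 5.3.4.2, 5.3.4.3 | No, survival only |
| Protocol 6.4 | Yes, to the final analysis |
| Protocol 7.1, general rule | Yes, to the final analysis, recurrence or secondary malignancy |
| Schedule footnote 14 | Yes, through the DFS follow-up period |
| SAP 6.2 | Yes, to an event or the final analysis |

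The last four continue scans by listing no stop at new therapy; none says so expressly. The conflict is nevertheless real, because the first row ends scans at that point.

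**2. Which analyses are touched if scans stop?**

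- Table 1 (primary) and Table 3 (investigator): unaffected. Both censor at the last scan before anti-tumor therapy.
- Table 4: affected. With no event it censors at the last IRC-reviewed scan. If imaging stops at new therapy, this is about the same scan as in Table 1. Deaths still count, and so do site-confirmed recurrences or secondary malignancies that the IRC oncologist confirms from pathology (Protocol 7.1.1 and 9.7; Table 4 note).
- Table 5: largely unaffected, since new therapy is itself the event. A patient whose scans stopped and who later died after two missed scans fits none of its rows cleanly.
- Table 7: possibly affected. It uses the midpoint to a later IRC-confirmed event, but these patients are censored either way, so only the censoring date moves.

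**3. Scans at stake per affected patient.** Inputs: 24-month accrual and 60-month maximum study period (Protocol Summary, SAP 3.3), and the Section 6.4 schedule of every 16 weeks from the withdrawal scan up to 3 years (156.5 weeks), then every 26 weeks from the first scan after 3 years. Follow-up runs from 60 − 24 = 36 months (last enrolled) to 60 months (first enrolled). The month of new therapy is assumed, and therapy is taken to start at the withdrawal scan.

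For month 12 (week 52.2), scans fall at weeks 68.2, 84.2, 100.2, 116.2, 132.2 and 148.2, which is 6 by month 36. Weeks 164.2, 190.2, 216.2 and 242.2 make 10 by month 60.

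| New therapy at (assumed) | Scans missed, 36 months' follow-up | Scans missed, 60 months' follow-up |
|---|---|---|
| Month 6 (week 26.1) | 8 | 12 |
| Month 12 (week 52.2) | 6 | 10 |
| Month 24 (week 104.4) | 3 | 7 |

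**4. Illustration of one unseen event.** Inputs: final boundary HR 0.773 and 245 events (SAP 6.3). This treats the HR as the ratio of event counts with exposure held fixed.

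- Axitinib events: 245 × 0.773 / 1.773 = 106.8. Placebo events: 245 / 1.773 = 138.2.
- One more on axitinib: 0.773 × 107.8 / 106.8 = 0.780, a shift of +0.007.
- One more on placebo: 0.773 × 138.2 / 139.2 = 0.767, a shift of −0.006.
- One more in each arm: 107.8 / 139.2, about 0.775 from unrounded counts, a shift of +0.002.

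This gives a sense of scale per event and is not a bound.

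**The case against.** The strongest reply is that Section 6.4 plainly governs. The Summary and Section 3 point to it, 7.1, footnote 14 and SAP 6.2 agree with it, and it provides for recording new anti-tumor therapy given for recurrence or secondary malignancy during follow-up. The two sentences sit in dosing guidance and are probably there to keep sites from dropping patients. SAP Section 1 also says that the SAP supersedes the protocol. As to intent, this is right. But the supersession clause governs analysis, not what a site does, and no clause ranks one protocol section above another. For a patient removed for toxicity, the narrower sentence is also the more specific instruction.

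The second reply is that almost nobody is affected. The patient must leave for toxicity, start new therapy without an IRC event, and be at a site that follows the narrower wording. After an investigator-called recurrence, 7.1 and 5.5.2 require that "the patient must continue to receive tumor assessments until the IRC determines recurrence or occurrence of a secondary malignancy". Need for other anticancer therapy is a separate withdrawal reason (6.5.1), and Protocol 1.2 says adjuvant treatment has no established role. All of this stands and keeps the point minor.

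The figures also have limits. The largest scan counts belong to patients who stay event-free to month 60, so they cannot describe the same patient as the HR shift. Table 4 removes censoring rules, so at the same cut-off it has at least as many events as the primary analysis; at the same HR, one event would then move it no more than shown.

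**Conclusion.** The point holds as a minor internal contradiction. Two operative sentences tell sites to stop scans that four other places require, and one pre-specified sensitivity analysis depends on those scans. The number of patients cannot be derived, because the documents give no rate of removal for toxicity or of new therapy without an IRC event. The per-patient loss of 3 to 12 scans rests on new therapy starting at month 6, 12 or 24 and on the planned 36 to 60 months of follow-up; the event-driven cut-off could change the latter. It also rests on reading new treatment as anti-tumor therapy, the natural sense, although 5.3.4.2 discusses new antihypertensive therapy nearby. There is no effect on the primary result, its boundaries, the event target or the sample size.

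**What to change.** In Protocol 5.3.4.2 and 5.3.4.3, delete the words that make the start of new treatment an end point for tumor assessments, or replace each sentence with a reference to Section 6.4. Notify sites by letter. The cost is an edit to two sentences and the letter. No scans are added beyond those that Section 6.4 already requires, and no endpoint, alpha level or sample size changes.
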